3.3.4.1 Withdrawal from trial treatment

An individual patient is to be withdrawn from trial treatment if:

- The patient wants to withdraw from trial treatment, without the need to justify the decision.
- The patient needs to take concomitant drugs that interfere with the investigational product. Refer to Section [4.2.2.2](#) for permitted and prohibited concomitant medications.
- The patient can no longer be treated with trial medication for other medical reasons (such as surgery, AEs, other diseases, or pregnancy). Refer to Section [4.1.4](#) for AEs that require treatment discontinuation.

Proprietary confidential information © 2021 Boehringer Ingelheim International GmbH or one or more of its affiliated companies

- The patient has repeatedly shown to be non-compliant with important trial procedures and, in the opinion of both, the investigator and sponsor representative, is not willing or able to stick to the trial requirements in the future.
- The patient experiences unequivocal PD by RECIST v1.1 and/or iRECIST.
- The patient completes 1 year of treatment. If the patient is benefiting clinically at 1 year, he/she may continue after a case-by-case review with the sponsor.

Given the patient's agreement, the patient will undergo the procedures for the end-of-treatment (EOT) visit and follow up as outlined in the [Flow Chart](#) and Section [6.2.3](#). For all patients the reason for withdrawal from trial treatment (e.g. AEs) must be recorded in the CRF. These data will be included in the trial database and reported.

During the dose finding part, patients withdrawn for a reason other than having a DLT or patients who miss more than one visit during MTD evaluation period may be replaced after discussion in the SMC if the information that needed to be collected during that visit is not available and makes the patient non-evaluable for the PK analyses or safety parameters (including evaluation for DLTs).

Patients who come off trial due to a DLT will not be replaced.

If a patient should become pregnant during the trial, the treatment with BI 754091 and BI 754111 must immediately be stopped. The patient will be followed up until delivery or termination of pregnancy (see Section [5.2.7.9](#) for information on pregnancy forms). The data of the patient will be collected and reported in the eCRF until the last patient's last visit and any events occurring thereafter will be reported in the BI drug safety database.

3.3.4.2 Withdrawal of consent for trial participation

Patients may withdraw their consent for trial participation at any time without the need to justify the decision.

This will however mean that no further information may be collected for the purpose of the trial and negative implications for the scientific value may be the consequence. Furthermore, it may mean that further patient follow up on safety cannot occur.

If a patient wants to withdraw consent, the investigator should explain the difference between treatment withdrawal and withdrawal of consent for trial participation and explain the options for continued follow up after withdrawal from trial treatment, please see Section [3.3.4.1](#) above.

3.3.4.3 Discontinuation of the trial by the sponsor

Boehringer Ingelheim reserves the right to discontinue the trial overall or at a particular trial site at any time for the following reasons:

1. Failure to meet expected enrolment goals overall or at a particular trial site
2. Emergence of any efficacy/safety information invalidating the earlier positive benefit-risk-assessment that could significantly affect the continuation of the trial

Proprietary confidential information © 2021 Boehringer Ingelheim International GmbH or one or more of its affiliated companies

3. Violation of GCP, the trial protocol, or the contract impairing the appropriate conduct of the trial
4. Completion of treatment by all patients and the sponsor determines that sufficient survival data has been collected.

The investigator / the trial site will be reimbursed for reasonable expenses incurred in case of trial termination (except in case of the third reason).

3.3.4.3.1 Enrolment stopping rules in case of unacceptable toxicities

All AEs, including serious adverse events (SAEs) and deaths will be carefully analysed by the sponsor. Unacceptable toxicity will be defined as:

- Clinically relevant adverse events that are:
 - unexpected considering the mode of action, and are not manifestations of underlying disease or background events typical of the trial population
 - and/or are debilitating, non-reversible, not manageable
 - or lead to a fatal outcomewhere evidence suggests that there was a reasonable possibility that the drug caused the adverse event.
- Higher than expected frequency or severity of adverse events (such as irAEs) that indicates those events occur more frequently or with higher severity in the drug treatment group than would be expected in the trial population.

If one or both of the above criteria are met the enrolment to the trial will be stopped to allow for in-depth analysis of the safety profile of the study medications. The benefit-risk profile of BI 754091 and/or BI 754111 will be re-assessed by the SMC. The outcome of the analysis and the recommendations will be shared with all involved regulatory health authorities prior to a possible re-start of enrolment. In case the benefit-risk assessment is no longer considered to be positive, the trial will be discontinued.

4. TREATMENTS

4.1 INVESTIGATIONAL TREATMENTS

4.1.1 Identity of the Investigational Medicinal Products

4.1.1.1 BI 754091

Details of the drug product, BI 754091 are presented in Table 4.1.1.1: 1. Additional details are presented in the BI 754091 IB and Pharmacy Manual.

Table 4.1.1.1: 1 BI 754091

Substance:	BI 754091
Pharmaceutical formulation:	Solution for infusion
Source:	Boehringer Ingelheim Pharma GmbH & Co. KG
Unit strength:	20 mg/mL
Posology	Infusion on Day 1 of each 3-week cycle
Route of administration:	I.V. infusion

4.1.1.2 BI 754111

Details of the drug product, BI 754111 are presented in Table 4.1.1.2: 1. Additional details are presented in the BI 754111 IB and Pharmacy Manual.

Table 4.1.1.2: 1 BI 754111

Substance:	BI 754111
Pharmaceutical formulation:	Solution for infusion
Source:	Boehringer Ingelheim Pharma GmbH & Co. KG
Unit strength:	20 mg/mL
Posology	Infusion on Day 1 of each 3-week cycle
Route of administration:	I.V. infusion

4.1.2 Selection of doses in the trial

4.1.2.1 Starting dose of BI 754091

BI 754091 will be tested at a flat starting dose of 240 mg to be administered via infusion q3w. In case of DLTs, lower doses may also be explored. The dose-finding will be guided by the BLRM, and the final decision will be made by the SMC (see Section [8.7](#)).

The starting dose was selected based on the data obtained in 1381-0001 dose-escalation cohorts, where 3 patients each received BI 754091 monotherapy at dose levels of 80, 240, and 400 mg and none of them experienced DLT or AESI and MTD was considered not reached and the RD was determined to be 240 mg.

The results of in vitro binding experiments suggest that BI 754091 has at least similar affinity to PD-1 as pembrolizumab ([n00250922](#)). Therefore, determining the dose based on the similarity of pharmacokinetic properties between BI 754091 and pembrolizumab is considered appropriate. The dose of pembrolizumab for PD-L1 positive, unresectable, advanced or recurrent NSCLC is 200 mg per dose at intervals of 3 weeks, which is similar to the starting dose of BI 754091 for Part I of this trial (240 mg). A comparison of the simulated pembrolizumab blood concentrations over time under 240 mg q3w dosing based on the population PK model ([R17-2460](#)) and the actual BI 754091 blood concentrations observed in the trial 1381-0001 (under the same dosing schedule) showed observed concentration of BI 754091 is mostly within the 90% prediction interval of simulated gMean of pembrolizumab. Hence BI 754091 240 mg appears to be appropriate and is expected to be effective in Asian patients. The preliminary results from trial 1381-0001 further showed that the binding of BI 754091 to the PD-1 receptors was saturated also support that the selected dose of 240mg q3w should be adequate.

Generally, antibody drugs, which are intravenously administered, are not metabolised via CYPs, and are not substrate of the transporter. Therefore, no differences in PK due to race and ethnicity are expected. Notable PK differences between Asian and Western patients have not been reported for similar drugs (anti-PD-1 antibodies including nivolumab and pembrolizumab). In fact, the dose and administration of similar drugs are comparable in Asian and non-Asian patients, which suggests that notable racial difference in PK is not expected with BI 754091 and justifies the determination of the starting dose in Asian patients by extrapolating the results in Western patients.

The exposure in a 13-week repeated dose toxicity study NOAEL (100 mg/kg) in cynomolgus monkeys (C_{max} : 6210 μ g/mL, AUC_{0-168} : 710000 μ g/mL h or AUC_{0-504} : 2130000 μ g/mL h) and the simulated steady state BI 754091 exposure following dosing of 240 mg q3w i.v. in humans (C_{max} : 110 μ g/mL, AUC_{0-504} : 29700 μ g/mL h based on predictions of the exploratory population pharmacokinetic BI 754091 model) showed the safety margin based on C_{max} and AUC_{0-504} to be 56-fold and 72-fold, respectively.

4.1.2.2 Starting dose of BI 754111

BI 754111 will be tested at a starting dose of 400 mg to be administered via infusion q3w. In case of DLTs in 400 mg cohort, lower doses may also be explored.

The starting dose was selected based on the data obtained in 1381-0002 dose-escalation cohorts. By the end of June 2018, BI 754111 was administered at dose range from 4 mg to 600 mg in combination with BI 754091 240 mg. DLTs were not reported at any dose level and the MTD was not reached.

Table 4.1.2.2: 1 Number of evaluable patients and DLTs in trial 1381-0002 (as of Jun 2018)

Dose level	BI 754091 dose	BI 754111 dose	Number of evaluable patients	Number of DLTs
1	240 mg	4 mg	3	0
2	240 mg	20 mg	9	0
3	240 mg	80 mg	9	0
4	240 mg	200 mg	9	0
5	240 mg	400 mg	9	0
6	240 mg	600 mg	9	0
Total	-	-	48	0

4.1.3 Dose-finding scheme

The dose is planned to be tested in cohorts at pre-defined provisional dose levels. The provisional dose levels to be assigned to separate cohorts of patients are listed in [Table 4.1.3: 1](#) and [4.1.3: 2](#). Intermediate or lower dose levels may be investigated if agreed in the SMC, depending on the number of DLTs observed in the trial.

In Part II, increasing doses of BI 754111 will be administered in combination with BI 754091 at the RD determined in Part I. The dose of BI 754091 may also be titrated based on DLTs and the overall safety profile of the combination.

Proprietary confidential information © 2021 Boehringer Ingelheim International GmbH or one or more of its affiliated companies

Table 4.1.3: 1 Example of dose titration in BI 754091 monotherapy dose finding part*

Dose level	Increment from previous dose	Proposed dose of BI 754091
-1	-66.6%	80 mg*
0	Starting dose	240 mg

Table 4.1.3: 2 Example of dose titration in combination dose finding part*

Dose level	Increment from previous dose	Proposed dose of BI 754111
-1	-50%	200 mg*
0	Starting dose	400 mg
1	50%	600 mg*
2	33.3%	800 mg*

*Actual dose assignments for individual patients will be communicated separately as determined by the SMC.

When the last patient in each cohort completes Cycle 1, the SMC will evaluate the available data. The SMC will review all safety data including, but not limited to, DLTs and all CTCAE Version 4.03 Grade ≥ 2 toxicity data during cycle 1. Updated safety data on other ongoing patients, including data beyond cycle 1, will be discussed as well. Based on that, a decision on the next dose level to be tested will be made.

4.1.4 Dose modifications and premedications

There will be no dose reductions or escalations of BI 754091 or BI 754111 in any one patient. The dose may be delayed for up to 6 weeks because of AEs, following discussion with the sponsor.

During combination therapy, if treatment is held or discontinued due to an AE(s), both BI 754091 and BI 754111 will be held or discontinued together. If treatment is to be restarted after resolution (\leq Grade 1 or baseline – exceptions should be discussed and agreed with the sponsor) of the AE, both BI 754091 and BI 754111 must be started together.

The study drug(s) should be permanently discontinued for Grade 3 to 4 pneumonitis, Grade 3 to 4 adrenal insufficiency, Grade 4 diabetes mellitus, any grade encephalitis, Grade 4 hypophysitis, Grade 4 rash, Grade 3 to 4 colitis or recurrent colitis of any grade, any recurrent Grade 3 to 4 irAEs, transaminase increases >5 times ULN or total bilirubin >3 times ULN (unless unequivocally attributed to another cause), inability to taper steroids to 10 mg or less prednisone or equivalent within 12 weeks, or persistent Grade 2 to 3 AEs (unless unequivocally attributed to another cause) that do not recover to Grade 1 or less within 12

Proprietary confidential information © 2021 Boehringer Ingelheim International GmbH or one or more of its affiliated companies

weeks. Study drug(s) should also be permanently discontinued for Grade 3 to 4 AEs that are classified as immune-related by the Investigator that are not listed in Appendix [10.1](#). Study drug(s) should be permanently discontinued if \geq Grade 4 drug-related AEs are reported. Please see Appendix [10.2](#) for guidelines for management of immune-related adverse events.

Infusion related reactions have been reported in approximately 7% of patients treated with the combination of BI 754091 and BI 754111, none reported with BI 754091 monotherapy. The majority of the events were reported in patients receiving 240 mg of BI 754091 in combination with 600 mg of BI 754111, with 2 events reported in patients receiving 240 mg of BI 754091 in combination with 20 mg of BI 754111. The majority were of CTCAE Grade 2. Two events were Grade 3 events and led to treatment discontinuation. The reported infusion related reactions occurred during the infusion mostly at cycle 2 or cycle 3. Symptoms of infusion related reactions may include, but not limited to, flushing, rigors, chills, dyspnea, nausea, vomiting, hypotension, hypertension, syncope, pruritus, tachycardia, and back pain.

To reduce the risk of IRRs, patients are to be premedicated with an antihistamine and acetaminophen or paracetamol. Premedications should be administered at sufficient time prior to initiation of infusion to allow the agents to exert their effect.

In the event of an infusion-related reaction \leq Grade 2, treat the symptoms accordingly with antihistamine or corticosteroids if needed, the infusion rate of study drug(s) may be decreased by 50% or interrupted until resolution of the event and re-initiated at 50% of the initial rate until completion of the infusion. In patients experiencing infusion-related reactions \leq Grade 2, subsequent infusions may be administered at 50% of the initial rate. If an infusion-related reaction is Grade 3 or higher in severity at any point during the study, permanently discontinue study drug(s) (see Section [5.2.7.5.3](#)).

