1.4 BENEFIT - RISK ASSESSMENT

The role of the immune-checkpoint inhibitors within a normal immune response is to dampen the immune response after the trigger (antigen) is resolved, minimizing collateral-immune-mediated damage to healthy tissue. Immune-checkpoint inhibitors also play a major role in promoting and maintaining self-tolerance by inactivating auto-reactive T-cells. Therefore, manipulation of immune-checkpoint-inhibitor pathways unleashes the immune system and comes with a higher risk of inducing immune dysfunction leading to immune-related adverse events (irAEs). Indeed, mice deficient in PD-1 or its ligands (PD-L1 and PD-L2) were found to be highly prone to development of autoimmune diseases ([R16-2362](#); [R16-2364](#); [R16-2968](#); [R16-2969](#); [R16-2970](#)).

Data from immune-checkpoint clinical trials show that irAEs occur frequently in patients treated with anti-CTLA-4 (90%) and anti-PD-1 or anti-PD-L1 (70%) mAbs. However, the majority of these AEs are mild in severity ([R12-5176](#); [R15-3588](#); [R15-3715](#)) and commonly occur within the first 4 months of initiating therapy ([R15-3780](#); [R16-0864](#); [R16-0899](#)). Immune-related AEs affect mainly the gastrointestinal tract (including diarrhoea and, less frequently colitis), skin (including rash/erythema and less frequently vitiligo), endocrine glands (including hypothyroidism, hyperthyroidism, and hypophysitis), liver (frequently asymptomatic elevated transaminases), and lung (pneumonitis), but could also potentially affect other tissues. Rare fatal cases of colitis, pneumonitis and myocarditis have been reported with use of immune-checkpoint inhibitors. The main treatment of irAEs is the administration of steroids for 2 to 4 weeks; other immunosuppressive agents (such as infliximab, mycophenolate mofetil and cyclosporine) can be used in case of steroid-refractory irAE ([R16-0763](#); [R16-0899](#)).

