5.2.7.5.2 Immune-related adverse events (irAEs)

Immune-related AEs are AEs associated with immunotherapy treatments that appear to be associated with the immune therapy’s mechanism of action. These adverse reactions, which can be severe, may involve the gastrointestinal, skin, liver, endocrine, respiratory, renal, or other organ systems. The sponsor has defined a list of irAEs in [Table 10.1: 1](#) that must be reported as AESIs. All immune-related events are to be reported as AEs. Some irAEs also need to be reported as AESIs as defined by the sponsor in [Table 10.1: 1](#). If an Investigator determines a Grade 3 event (not on the list) to be immune-related, the Investigator should also report that event as an AESI.

Recommendations for the management of irAEs are presented in Appendix [10.2](#).

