Renal (report as AESI if an irAE is \geq Grade 2)

- Nephritis
- Nephritis autoimmune
- Renal failure
- Renal failure acute
- Creatinine elevations (report as an irAE if \geq Grade 3 or any grade resulting in dose modification or use of systemic steroids to treat the AE)

Skin (report as AESI for any grade)

- Dermatitis exfoliative
- Erythema multiforme
- Stevens-Johnson syndrome
- Toxic epidermal necrolysis

Skin (report as AESI if an irAE is \geq Grade 3)

- Pruritus
- Rash
- Rash generalized
- Rash maculopapular
- Any rash considered clinically significant in the physician's judgment

Other (report as AESI for any grade)

- Myocarditis
- Pancreatitis
- Pericarditis
- Any other Grade 3 event that is considered immune-related by the physician

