10.2 MANAGEMENT OF IMMUNE-RELATED ADVERSE EVENTS

Management of immune-related adverse event toxicities associated with anti-PD-1 mAbs are presented below. **BI 754091 and BI 754111 should be permanently discontinued for Grade 3-4 pneumonitis, Grade 3-4 adrenal insufficiency, Grade 4 diabetes mellitus, any grade encephalitis, Grade 4 hypophysitis, Grade 4 rash, Grade 3-4 or recurrent colitis of any grade, any recurrent Grade 3-4 AE, transaminase increased >5 times ULN or total bilirubin >3 times ULN (unless unequivocally attributably to another cause), inability to taper steroids to 10 mg or less prednisone or equivalent within 12 weeks, or persistent Grade 2-3 AEs that do not recover to Grade 1 or less within 12 weeks.**

- Pneumonitis:
 - For Grade 2 events, treat with systemic corticosteroids. When symptoms improve to Grade 1 or less, steroid taper should be started and continued over no less than 28 days.
 - Add prophylactic antibiotics for opportunistic infections in the case of prolonged steroid administration.
 - For Grade 3-4 events immediately treat with i.v. steroids. Administer additional anti-inflammatory measures, as needed.
 - BI 754091 and BI 754111 should be permanently discontinued for Grade 3-4 pneumonitis, inability to taper steroids to 10 mg or less prednisone or equivalent within 12 weeks, or persistent Grade 2 AEs that do not recover to Grade 1 or less within 12 weeks.
- Diarrhoea/Colitis:

Subjects should be carefully monitored for signs and symptoms of enterocolitis (such as diarrhoea, abdominal pain, blood or mucus in stool, with or without fever) and of bowel perforation (such as peritoneal signs and ileus).

 - All subjects who experience diarrhoea/colitis should be advised to drink liberal quantities of clear fluids. If sufficient oral fluid intake is not feasible, fluid and electrolytes should be substituted via i.v. infusion. For Grade 2 or higher diarrhoea, consider GI consultation and endoscopy to confirm or rule out colitis.
 - For Grade 2 diarrhoea/colitis that persists greater than 3 days, administer oral corticosteroids.
 - For Grade 3 or 4 diarrhoea that persists >1 week, treat with i.v. steroids followed by high-dose oral steroids.
 - For Grade 3 or 4 colitis, or recurrent colitis of any grade, permanently discontinue BI 754091 and BI 754111, and immediately treat with i.v. steroids followed by high-dose oral steroids.

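### The Section 4.1.4 stop for unlisted Grade 3–4 immune-related events defeats itself at Grade 3, and a first resolving Grade 3 myocarditis has no mandatory event-specific stop

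*Protocol*

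**What the plan says.** Protocol Section 4.1.4 holds the permanent-stop rules. It begins "The study drug(s) should be permanently discontinued for Grade 3 to 4 pneumonitis" and goes on through other named events, among them "Grade 3 to 4 colitis or recurrent colitis of any grade". It then adds general stops: a recurrent Grade 3–4 immune-related event, a steroid taper that fails within 12 weeks, and a Grade 2–3 event that persists beyond 12 weeks. After these comes the clause at issue, which refers to Appendix 10.1: treatment "should also be permanently discontinued for Grade 3 to 4 AEs that are classified as immune-related by the Investigator that are not listed in" that appendix. The next sentence stops drug when at least "Grade 4 drug-related AEs are reported".

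Table 10.1:1 in Appendix 10.1 defines which immune-related events must be reported as AESIs. Its final group names myocarditis, pancreatitis and pericarditis, and then adds "Any other Grade 3 event that is considered immune-related by the physician".

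Appendix 10.2, on managing immune-related events, opens with its own stop list ("BI 754091 and BI 754111 should be permanently discontinued for Grade 3-4 pneumonitis, Grade 3-4 adrenal insufficiency", and so on). It then gives guidance by organ, with no cardiac entry.

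Section 1.4 says: "Rare fatal cases of colitis, pneumonitis and myocarditis have been reported with use of immune-checkpoint inhibitors".

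**The concern.** Two things go wrong when the sections are read together.

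First, a stopping rule is defined by absence from a table that was written for reporting and that ends with a catch-all. If the catch-all counts as a listing, every Grade 3 immune-related event is listed and the clause can never apply at Grade 3. If it does not count, the clause applies to every Grade 3 event not named in the table. A site has to choose, and the choice decides whether a patient stops for good or may restart.

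Second, the clause cannot reach an event that the table does name. Myocarditis is named, and neither stop list gives it a line. A first Grade 3 case that recovers may therefore be re-treated, while an unnamed first Grade 3 event must stop on the more likely reading.

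At stake are patient safety and, to a small degree, consistent counting of AEs leading to treatment discontinuation, which SAP Section 7.8.1 tabulates.

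**Working it through.** No sample size, error rate or event count is involved, so the check sets the rules side by side and follows a patient through them.

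**Step 1: what the clause covers.**
- *Literal reading.* The catch-all row in Table 10.1:1 takes in all remaining Grade 3 immune-related events, so no Grade 3 event is unlisted. The row does not mention Grade 4, so unnamed Grade 4 events stay within the clause. The next sentence of 4.1.4, on drug-related events of Grade 4 or higher, nearly duplicates that part.
- *Not-named reading.* The clause covers every Grade 3–4 immune-related event that the table does not name. Section 5.2.7.5.2 supports this: "If an Investigator determines a Grade 3 event (not on the list) to be immune-related". It cites Table 10.1:1 and still treats such an event as off the list. That section concerns AESI reporting, however, and 4.1.4 does not refer to it.

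**Step 2: a first Grade 3 myocarditis that resolves and tapers in time to restart within the permitted delay.** Going through 4.1.4 and Appendix 10.2:
- event-specific stop: none;
- clause for unlisted events: not triggered, because myocarditis is named in Table 10.1:1;
- recurrent Grade 3–4 event: not triggered, because this is a first event;
- 12-week persistence or failed taper: not triggered;
- Grade 4 or higher drug-related event: not triggered;
- Appendix 10.2 opening list and organ entries: nothing on myocarditis.

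What does apply is general. Dosing may be held for up to 6 weeks after discussion with the sponsor, and both drugs may restart together at Grade 1 or less, or baseline.

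**Step 3: outcomes compared.**

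| First event at Grade 3 | Clause read literally | Clause read as not named |
|---|---|---|
| Immune-related event not named in Table 10.1:1 | No mandatory stop | Permanent stop |
| Myocarditis, resolving | No mandatory stop | No mandatory stop |
| Colitis or pneumonitis | Permanent stop (own line) | Permanent stop (own line) |

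The first row shows the two readings giving opposite actions. The second shows that neither reading helps for myocarditis. Of the three events that Section 1.4 names as having fatal cases, two have a Grade 3–4 stop in both 4.1.4 and the opening list of 10.2. The remaining 3 − 2 = 1, myocarditis, has it in neither.

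**Step 4: does other text close the gap?**
- Section 3.3.4.1 allows withdrawal for medical reasons, but refers back to 4.1.4 for the AEs that require it.
- The DLT definition in 4.1.5 does not itself order discontinuation, and it exempts a Grade 3 immune-related event that resolves with immunosuppressive therapy within 2 weeks.
- AESI reporting at any grade and the scheduled troponin tests help detect the event but set no stopping rule.

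**The case against.** The strongest reply is that nobody would operate the literal reading, because it empties the clause at Grade 3. Section 5.2.7.5.2 shows what the authors meant, so this half is a drafting clarification. That is largely right about intent. It does not remove the defect, because 4.1.4 is where sites look for stop rules and it does not state the intended meaning.

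A reader might infer that the protocol has no rule at all for Grade 3 myocarditis. The documents do not support that. The hold, the sponsor discussion, the recovery condition for restart, the stops for recurrence, persistence and failed taper, and medical withdrawal all apply. A drug-related Grade 4 case must stop, and myocarditis of any grade goes to the sponsor on the SAE timeline. Only a mandatory, event-specific stop for a first, resolving Grade 3 case is missing.

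It is also fair to say that Section 1.4 is class background and not the basis of the stop list: encephalitis and adrenal insufficiency have stops without being named there as having fatal cases. Section 1.4 therefore does not oblige the protocol to stop every event with fatal cases at first Grade 3. It does make the different treatment of myocarditis stand out, and the documents give no reason for it.

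Finally, other severe events named in Table 10.1:1 are in the same position, for example Guillain-Barre syndrome, myasthenic syndrome, Stevens-Johnson syndrome, toxic epidermal necrolysis, pancreatitis and pericarditis. This stands, and it bears on how far the fix should reach.

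**Conclusion.** The point holds and is minor. The clause in 4.1.4 is a self-defeating cross-reference at Grade 3. Its likely meaning can be inferred from 5.2.7.5.2 but is not stated where it is needed. On either reading, a first Grade 3 myocarditis that resolves may restart, while colitis and pneumonitis of the same grade may not.

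This rests on taking the current text of 4.1.4, 10.1 and 10.2 as written. The documents give no rate of Grade 3 myocarditis, so the number of patients affected cannot be computed. A reader might suspect an effect on the MTD or on objective response; nothing in the documents shows one, and none is claimed. The absence of the clause from Appendix 10.2 matters little by itself, because 4.1.4 states the stop and cites 10.2 only for management guidance.

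**What to change.** 1. In 4.1.4, define the events covered by the clause as those *not named in Table 10.1:1*, expressly excluding its row "Any other Grade 3 event that is considered immune-related by the physician".
2. Add Grade 3 to 4 myocarditis to the permanent-stop list in 4.1.4 and to the list that opens Appendix 10.2.
3. Optionally, state in 10.2 that the stop rules of 4.1.4 govern. Copying over the two stops that 10.2 lacks (this clause and the Grade 4 drug-related stop) would not make the lists match. They would still differ on recurrent events (immune-related events in 4.1.4, any AE in 10.2), on the exception for persistent events clearly due to another cause (4.1.4 only), and on the Grade 3 infusion-reaction stop (4.1.4 only).

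With steps 1 and 2 alone, the other named severe events without a stop line stay under the general provisions. If the sponsor wants those covered too, the reference in step 1 can be to events *not named in 4.1.4 or Appendix 10.2*.

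The cost is a wording amendment, which under Section 8.1 needs IRB/IEC and authority approval. A few patients who might have restarted after a first Grade 3 myocarditis would stop instead. No new data, visits or patients are needed.
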